4. SUBJECT POPULATION

The inclusion and exclusion criteria for enrolling subjects in this study are described in the following subsections. These criteria are consistent with those for recent interventional studies in newly diagnosed T1D, the targeted subject age range in this study, and recent studies of golimumab for other indications. If there is a question about the inclusion or exclusion criteria below, the investigator must consult with the appropriate sponsor representative and resolve any issues before enrolling a subject in the study. Waivers are not allowed. Deviations from the inclusion and exclusion criteria are not allowed because they can potentially jeopardize the scientific integrity of the study, and subject safety. Therefore, adherence to the criteria as specified in the protocol is essential.

Individuals who meet entry criteria but are not able to be randomized within the allotted time (ie, 28 days from screening) may still participate in the study so long as they repeat study screening and again meet eligibility criteria. Subjects may only be rescreened once.

If a subject is a screen failure but at some point, in the future is expected to meet the subject eligibility criteria, the subject may be rescreened on 1 occasion only after consultation with the sponsor.

Subjects who are rescreened will be assigned a new subject number, undergo the informed consent/assent process, and then restart a new screening phase.

Retesting of abnormal screening values that lead to exclusion is allowed only once using an unscheduled visit during the screening period to reassess eligibility. This should only be considered if there is no anticipated impact on subject safety.

If a subject's status changes (including laboratory results or receipt of additional medical records) after screening but before the first dose of study agent is given such that they no longer meet all eligibility criteria, they should be excluded from participation in the study.

4.1. Inclusion Criteria

4.1.1. Inclusion Criteria Applicable to All Subjects

Each potential subject must satisfy all of the following criteria to be enrolled in the study:

1. Male or female 6 through 21 years of age who are diagnosed with T1D within 100 days of randomization per the ADA standard T1D criteria.⁷⁰
2. Be positive for at least 1 of the following diabetes-related autoantibodies obtained at study screening:
 - Glutamic acid decarboxylase (GAD-65)
 - IA-2
 - ZnT8
 - ICA; or
 - Insulin (if obtained within 10 days of the onset of exogenous insulin therapy)
3. Have a peak stimulated C-peptide level ≥ 0.2 pmol/mL following a 4-hour MMTT obtained at study screening.
4. Be medically stable on the basis of physical examination, medical history, and vital signs performed at screening. If there are abnormalities, they must be consistent with the underlying illness in the study population.
5. Females of childbearing potential must have a negative serum (β -human chorionic gonadotropin [β -hCG]) test at screening and a negative urine pregnancy test at the Week 0 visit.
6. Criterion modified per Amendment 3 – open-label extension period
 - 6.1. Females must be either:
 - Not of childbearing potential: premenarchal; permanently sterilized (eg, tubal occlusion, hysterectomy, bilateral salpingectomy); or otherwise be incapable of pregnancy,

OR

- Of childbearing potential, and if sexually active, practicing through Week 104 and open-label extension period of the study be practicing a highly effective method of birth control consistent with local regulations regarding the use of birth control methods for subjects participating in clinical studies: eg, established use of oral, injected or implanted hormonal methods of contraception; placement of an intrauterine device (IUD) or intrauterine system (IUS); barrier methods: condom with spermicidal foam/gel/film/cream/suppository or occlusive cap (diaphragm or cervical/vault caps) with spermicidal foam/gel/film/cream/suppository; male partner sterilization (the vasectomized partner should be the sole partner for that subject); true abstinence (when this is in line with the preferred and usual lifestyle of the subject).
- Females of childbearing potential must agree not to donate eggs (ova, oocytes) for the purposes of assisted reproduction through Week 104 and open-label extension period.

Note: If the childbearing potential changes after start of the study (eg, female who is not heterosexually active becomes active, premenarchal female experiences menarche) she must begin a highly effective method contraception of birth control, as described throughout the inclusion criteria.

- Agrees to remain on a highly effective method of birth control throughout the study.
7. During the treatment period of the study (from randomization through Week 52) and for a minimum of 1 spermatogenesis cycle (defined as 90 days after receiving the last dose of study agent), all males must:
- Agree to be sexually abstinent or (2) if sexually active with a non-pregnant female of childbearing potential must agree to use a barrier method of contraception (eg, condom with spermicidal foam/gel/film/cream/suppository) and if sexually active with a female who is pregnant must use a condom.
 - Agree not to donate sperm.
8. Subjects (or their legally acceptable representatives) are willing and able to adhere to requirements, prohibitions, and restrictions specified in this protocol.
9. Subjects (or their legally acceptable representative) must sign an ICF indicating that he or she understands the purpose of, and procedures required for, the study and is willing to participate in the study. Assent is also required of children capable of understanding the nature of the study (typically 7 years of age and older) as described in Section 16.2.3, Informed Consent and Assent Form.

10. Subjects (or their legally acceptable representative) must sign a separate informed consent form if he or she agrees to provide an optional DNA sample for research. Refusal to give consent/assent for the optional DNA research sample does not exclude a subject from participation in the study. Assent is also required of children capable of understanding the nature of the study (typically 7 years of age and older) as described in Section 16.2.3, Informed Consent and Assent form.
11. Prior to receiving the study agent, subjects must be up-to-date with and agree to receive routine age-appropriate immunizations according to current Centers for Disease Control and Prevention (CDC) guidelines and agree to comply with the guidelines for immunosuppressed individuals and those with chronic disease (diabetes mellitus). Specific to the human papillomavirus (HPV) vaccine, pneumococcal vaccine and any non-routine vaccines for immunosuppressed individuals or those with chronic diseases, subjects must have received these immunizations or initiated the recommended vaccine series and have a completion plan before the first administration of study agent. Documentation of required immunizations or proof of corresponding immunity (eg, vaccination card, medical record, or demonstration of protective antibody titers) must be provided to the study site.

4.1.2. Additional Inclusion Criteria for Responders

Each responder must also satisfy the following criteria to be eligible to restart active treatment:

1. Subjects must meet the MMTT criteria at Screening for the open-label extension period. If the most recent MMTT is <3 months ago, a repeat MMTT is not required. Subjects who had their most recent safety laboratory samples drawn within 1 month prior to screening do not need a repeat; eligibility will be assessed based on these most recent laboratory tests. For C-responders who are lacking the necessary information to calculate IDAA1c score, an HbA1c will be performed and 10 days of insulin dose information will be required.

4.2. Exclusion Criteria

4.2.1. Exclusion Criteria applicable to All Subjects

Any potential subject who meets any of the following criteria will be excluded from participating in the study:

Coexisting medical conditions or past medical history:

1. Has a history of significant renal, vascular, pulmonary, gastrointestinal, neurologic, hematologic, rheumatologic, or psychiatric disease.
2. Has significant cardiovascular disease, including history of myocardial infarction, congestive heart failure, angina, abnormal electrocardiogram or abnormal stress test.
3. Has a disease associated with lymphopenia, malignancy, bone marrow or organ transplantation, lymphoproliferative disorder, immune deficiency syndrome (eg,

severe combined immunodeficiency syndrome, T-cell deficiency syndromes, B-cell deficiency syndromes, or chronic granulomatous disease).

4. Has another autoimmune disease (eg, RA, pJIA, PsA, AS, MS, systemic lupus erythematosus [SLE], celiac disease [clinically symptomatic and antibody positive, ie, tissue transglutaminase IgA]). excluding clinically stable autoimmune thyroiditis whether treated or untreated.
5. Has nervous system disorder including but not limited to Guillain-Barre Syndrome, multiple sclerosis (MS), or progressive multifocal leukoencephalopathy (PML).
6. Has known allergies, intolerance and/or hypersensitivity to human immunoglobulin proteins, golimumab or any of its components or its excipients, or a known allergy or severe sensitivity to latex (refer to the SIMPONI and VarioJect Investigator's Brochures).^{35,36}
7. Has any of the following hematologic abnormalities at screening, confirmed by repeat tests at least 1 week apart:
 - White blood count <3,500/ μ L or >14,000/ μ L;
 - Platelet count <100,000 / μ L; or
 - Hemoglobin <10 g/dL.
8. Has a diagnosis of liver insufficiency or disease or hepatic enzymes equal to or above the values below, which represent alanine aminotransferase (ALT) and aspartate aminotransferase (AST) ≥ 2 times the upper limit of the gender- and age-based upper limit of normal confirmed by a repeat test at least 1 week apart (These values are based on the Central Laboratory normal ranges of AST and ALT values ([Attachment 5](#)))

Aspartate aminotransferase (AST)

Females

- 96 U/L (age 6)
- 80 U/L (age 7 through 17)
- 68 U/L (age 18 and above)

Males

- 118 U/L (age 6)
- 80 U/L (age 7 through 17)
- 72 U/L (age 18 and above)

Alanine aminotransferase (ALT)*Females*

- 68 U/L (age 6 and above)

Males

- 68 U/L (age 6 through 9)
- 86 U/L (age 10 and above)

Infections or predispositions to infections

9. Has active infections, is prone to infections or has chronic, recurrent or opportunistic infectious disease, including but not limited to, chronic renal infection, chronic chest infection (eg, bronchiectasis), sinusitis, recurrent urinary tract infection (eg, recurrent pyelonephritis, chronic cystitis), *Pneumocystis carinii*, aspergillosis, latent or active granulomatous infection, histoplasmosis, or coccidioidomycosis or an open, draining, or infected non-healing skin wound or ulcer.

10. Has any of the following TB screening criteria:

- A history of latent or active TB prior to screening.
- Signs or symptoms suggestive of active TB upon medical history and/or physical examination.
- Recent close contact with a person with known or suspected active TB.
- A history of or a positive QuantiFERON[®]-TB Gold test result at screening (see [Attachment 1](#)).

A subject whose first QuantiFERON-TB Gold test result is indeterminate should have the test repeated. In the event that the second QuantiFERON-TB Gold test result is also indeterminate, the subject should be excluded from the study. Subjects with a negative QuantiFERON-TB Gold test result are eligible to continue with pre-randomization procedures.

11. Has a clinically active infection with Epstein-Barr virus (EBV) or an EBV viral load $\geq 10,000$ copies per mL of plasma obtained at study screening.

12. Has a clinically active infection with cytomegalovirus (CMV) or a CMV viral load $\geq 10,000$ copies per mL of plasma obtained at study screening.

13. Is infected with human immunodeficiency virus (HIV), hepatitis B (HBV) or hepatitis C (HCV) or at screening tests positive for HIV, HBV (See [Attachment 4](#) for guidance for HBV test interpretation), or HCV.

Concomitant or previous medical therapies received:

14. Current or prior (within 30 days of screening) treatment that is known to cause a significant, ongoing change in the course of T1D or immunologic status, including high-dose inhaled, extensive topical, or systemic glucocorticoids.
15. Current or prior (within 30 days of screening) use of anti-hyperglycemic agents, including but not limited to metformin, sulfonylureas, glinides, thiazolidinediones, exenatide, liraglutide, DPP-IV inhibitors or amylin.
16. Current or prior (within 30 days of screening) use of any medication known to influence glucose tolerance including but not limited to atypical antipsychotics, diphenylhydantoin, thiazide, or other potassium-depleting diuretics, β -adrenergic blockers, or niacin.
17. Has ever received a systemic immunosuppression medicine or immune modulatory biologic therapy, including but not limited to T- or B-cell depleting therapy.
18. Has received or is expected to receive any live viral or live bacterial vaccinations from 90 days before first study agent administration, during the treatment period, and up to 120 days after the last study agent administration.
19. Has had a Bacille Calmette-Guérin (BCG) vaccination within 12 months of screening or is planned to receive BCG vaccination during the treatment period, and up to 12 months following last study agent administration.

Reproductive

20. If female, is pregnant, lactating, or breastfeeding, or planning to become pregnant while enrolled in this study.
21. If male, plans to father a child while enrolled in this study.

General Restrictions

22. Criterion modified per Amendment 3 – open-label extension period
 - 22.1. Has participated in any interventional clinical study within the 6 months prior to enrollment or is currently enrolled in an investigational study (apart from CNTO148DML2001 trial).
23. Criterion modified per Amendment 3 – open-label extension period
 - 23.1. Has received an investigational drug (including investigational vaccines) or used an invasive investigational medical device within 90 days before the planned first dose of study agent or is currently enrolled in an investigational study (apart from

CNTO148DML2001 trial).

24. Has any condition for which, in the opinion of the investigator, participation would not be in the best interest of the subject (eg, compromise the well-being) or that could prevent, limit, or confound the protocol-specified assessments.

NOTE: Investigators should ensure that all study enrollment criteria have been met at screening and, at randomization. If a subject's clinical status changes (including any available laboratory results or receipt of additional medical records) after screening but before randomization and the first dose of study agent is given such that he or she no longer meets all eligibility criteria, then the subject should be excluded from participation in the study. Section 9.1.2, Screening Period, describes options for retesting. Section 17.4, Source Documentation, describes the required documentation to support meeting the enrollment criteria.

4.2.2. Additional Exclusion Criteria for Responders

1. Subjects having reported clinically significant AEs or serious adverse event (SAEs) deemed to be related to the study agent during the double-blind period (e.g. severe infections or hypersensitivity reactions), precluding renewed exposure to golimumab.
2. Subjects who discontinued study agent administration prior to Week 52 or who have completed the Week 104 visit of the double-blind period or discontinued early from the study.
3. Subjects and/or caregivers who are unwilling or unable to administer study agent.

4.3. Exceptions to Inclusion and Exclusion Criteria for Open-Label Extension Period

The responders must continue to meet the initial inclusion and exclusion criteria to be eligible for the open-label extension period with following exceptions:

1. Autoantibody status will not be assessed (refer to criteria 2 under Section 4.1.1).
2. Subjects older than 21 years of age are eligible (refer to criteria 1 under Section 4.1.1).
3. For the open-label extension period, subjects may begin open-label study agent while EBV polymerase chain reaction (PCR) results are pending and if he/she meets all other inclusion/exclusion criteria. If EBV PCR results come back positive, subject must immediately stop treatment and be withdrawn from the study.

4.4. Prohibitions and Restrictions

Potential subjects must be willing and able to adhere to the following prohibitions and restrictions during the course of the study to be eligible for participation:

1. Refer to Section 8 for details regarding prohibited and restricted therapy during the study.

2. Agree to follow the contraceptive requirements as noted in the inclusion criteria.
3. Criterion modified per Amendment 3 – open-label extension period
 - 3.1. Will not receive a live virus or live bacterial vaccination 90 days before first study agent administration, during the 52-week treatment period and the open-label extension period of the study and up to 120 days after the last study agent administration.
4. Criterion modified per Amendment 3 – open-label extension period
 - 4.1. Will not receive a BCG vaccination within 12 months of screening, during the 52-week treatment period and the open-label extension period of the study and up to 12 months following last study agent administration.
5. Criterion modified per Amendment 3
 - 5.1. If sexually active and of childbearing potential, females will remain on a highly effective method of birth control and must not donate eggs (ova, oocytes) for the purposes of assisted reproduction throughout the study, or if she withdraws early from the study within 6 months of the last study agent administration.
6. Criterion modified per Amendment 3 – open-label extension period
 - 6.1. If sexually active with a female of childbearing potential and has not had a vasectomy, males must use a double barrier method of birth control during the study. Males must not donate sperm and must agree not to plan a pregnancy or father a child during the 52-week treatment period and the open-label extension period of the trial and for 90 days after the last study agent administration, or if he withdraws early from the study within 90 days of the last study agent administration.
7. Criterion modified per Amendment 3
 - 7.1. Must not receive investigational drugs, systemic immunosuppressants (including, but not limited to cyclophosphamide) or other biologics throughout the study.

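### Women who complete the open-label extension appear to be released from the contraception and egg-donation limits about 10 weeks after their last dose, 16 weeks short of the 6 months asked of early withdrawers

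*Protocol*

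**What the plan says.** Three places in the Protocol set the female limits.

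- Section 4.4, item 5.1: contraception and the bar on egg donation apply "throughout the study, or if she withdraws early from the study within 6 months of the last study agent administration".
- Section 4.1.1, criterion 6.1: egg donation is barred "for the purposes of assisted reproduction through Week 104 and open-label extension period", contraception has the same end point, and a closing bullet reads "Agrees to remain on a highly effective method of birth control throughout the study".
- Section 4.2.1, exclusion 20: excludes a woman "planning to become pregnant while enrolled in this study".

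The 6 months in item 5.1 are the only female interval counted from the last dose, and they are tied to early withdrawal.

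The neighbouring items in Section 4.4 are built differently. Live vaccines are barred during "the open-label extension period of the study and up to 120 days after the last study agent administration", BCG during "the open-label extension period of the study and up to 12 months following last study agent administration", and sperm donation or fathering a child during "the open-label extension period of the trial and for 90 days after the last study agent administration". Each names the extension and then counts from the last dose for every subject.

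On timing, Section 9.1.5.3 puts the last extension dose at Week 50 and the post-treatment visit at OL Week 60 or 10 weeks after the last dose. Section 10.1 treats a subject as having completed at Week 104 or at OL Week 60. In the double-blind period the last dose is at Week 52 (Section 9.1.3.3) and follow-up runs to Week 104.

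**The concern.** The limits guard against fetal exposure. In the double-blind schedule a completer is bound well beyond 6 months after her last dose, so a 6-month clause for early leavers works as a floor. In the extension the order reverses: the completer, who has received the full course, is bound for less time than the woman who leaves early. Two women whose last extension dose falls on the same date would be released about 16 weeks apart, and the one with the shorter protection is the one who followed the protocol to the end.

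Early withdrawal from the extension is foreseeable. Section 4.3 says "If EBV PCR results come back positive, subject must immediately stop treatment and be withdrawn from the study", and Section 10.2 withdraws responders whose remission score deteriorates. Section 10.2 also gives women who stop dosing an end-of-study visit and a further visit 10 weeks later, without saying whether such a woman counts as an early withdrawer under item 5.1. A site would have to guess which interval to give her.

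**Working it through.** **Inputs.** Last extension dose: OL Week 50, dosing window ±3 days (Sections 9.1.5.3 and 7.1.2.1). Post-treatment visit: OL Week 60, Day 421 ±7 days (open-label Time and Events Schedule). Early-withdrawal interval: 6 months (item 5.1), taken here as 182 days.

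**The plan's own figure.** OL Week 50 is Day 50 × 7 + 1 = 351. Then 421 − 351 = 70 days = 10 weeks, which agrees with Section 9.1.5.3.

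**Windows.** Shortest: (421 − 7) − (351 + 3) = 60 days. Longest: (421 + 7) − (351 − 3) = 80 days.

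**Shortfall against 6 months.** 182 − 70 = 112 days = 16 weeks. With the windows: 182 − 80 = 102 to 182 − 60 = 122 days. If 6 months is read as 24 weeks (168 days), the shortfall is 98 days = 14 weeks.

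**Does Week 104 in criterion 6.1 lengthen the interval?** No. Restart comes after Week 52, so OL Week 60 falls no earlier than about Week 52 + 60 = 112.

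**Double-blind completers.** (104 − 52) × 7 = 364 days, well beyond 6 months.

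**Time still to run at OL Week 60 under each rule, for a completer:**

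| Rule (Section 4.4) | Interval after last dose | Days left at OL Week 60 (range) |
|---|---|---|
| Live vaccines, item 3.1 | 120 days | 120 − 70 = 50 (40 to 60) |
| BCG, item 4.1 | 12 months (365 days) | 365 − 70 = 295 (285 to 305) |
| Sperm donation or fathering, item 6.1 | 90 days | 90 − 70 = 20 (10 to 30) |
| Female limits, item 5.1 | none for completers | 0 |

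**Other readings of when the study ends.**

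- Section 12.4.1 has a parenthesis that equates the end of the study with 52 weeks after the last dose. That would close the gap, but it fits only the double-blind schedule. Applied to the extension it gives OL Week 50 + 52 = 102, which is 42 weeks after the completion point in Section 10.1.
- Section 17.9.1 ends the study at the last subject's last visit. A woman's interval would then depend on other subjects. She would reach 182 days only if her OL Week 60 visit came at least 112 days before that last visit, and the last completer would still have about 10 weeks.

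Neither reading matches criterion 6.1, which ends with the extension period.

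**The case against.** The strongest reply is that this is a drafting query with no demonstrated hazard. Nothing in the documents says why 6 months was chosen or that 10 weeks is too short. The plan uses about 10 weeks as its close-out point elsewhere: the post-treatment visit, and the early End of Study visit in Section 10.2. A urine pregnancy test is scheduled at OL Week 52 and again at OL Week 60. New consent and assent forms are required for the extension, and they and the Investigator's Brochure are not available here; either may give an interval or a reason. All of this stands and keeps the point minor. It does not close the gap: a test at OL Week 60 says nothing about conception afterwards, and the Protocol text still sets a shorter interval than its own 6 months.

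Some stronger conclusions that a reader might draw are not supported.

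- **That any difference between completers and withdrawers is a defect.** Double-blind completers are bound for 364 days against about 182 for early withdrawers, and that does no harm. The issue is only that extension completers fall below 6 months.
- **That 10 weeks exposes a fetus to risk.** The documents contain no evidence either way.
- **That Amendment 3 overlooked the shorter tail.** The change log records that item 5 was reworded to accommodate the extension. A one-line log cannot show what was considered.
- **That the male rule sets the standard.** Criterion 7 ties the 90 days to a spermatogenesis cycle, and the barrier method in item 6.1 applies only during the study.
- **That the number of women can be estimated.** The documents give no shares for response, sex, childbearing potential or uptake. The egg-donation limit in criterion 6.1 also covers women of childbearing potential who are not sexually active.

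**Conclusion.** The point holds as a minor inconsistency in a participant-safety rule. Taking completion at OL Week 60 (Section 10.1) and the end point in criterion 6.1 at face value, a woman of childbearing potential who completes the extension is bound for about 70 days after her last dose (60 to 80). That is about 16 weeks less than the only female post-dose interval the Protocol states.

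The conclusion assumes that the study ends for her at OL Week 60, which is the most natural reading but not the only possible one, and that 6 months means about 182 days. Whether women in the extension are in practice told a longer interval depends on a consent form not seen here. The number affected is unknown and must be small, since only golimumab-treated responders from 54 planned golimumab subjects can enter the extension. No endpoint, estimate or test is affected.

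**What to change.** In item 5.1 of Section 4.4 and criterion 6.1 of Section 4.1.1, state that contraception and the egg-donation limit apply throughout the study and for at least 6 months after the last dose of study agent, whichever is later, for completers and early withdrawers alike. A woman last dosed at OL Week 50 would then be bound to about OL Week 76 (50 + 26). Double-blind completers would keep their cover to Week 104. The question of who counts as an early withdrawer would no longer matter for this rule. Align the extension consent and assent forms if they do not already say this.

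The cost is a wording change in two sections and possibly in the forms. No visit or procedure is added; the vaccine items already rely on undertakings that run past OL Week 60. The downside is about 16 more weeks of contraception for a few women, without a pharmacological need demonstrated in these documents.
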